### 4.2 Analysis Populations

#### 4.2.1 Screened Set (SS)

All patients who sign the informed consent form.

#### 4.2.2 Full Analysis Set (FAS)

All patients who are randomised. Patients will be analysed according to the randomised treatment.

#### 4.2.3 Modified Full Analysis Set (MFAS)

All patients who are randomised and returned for at least one post-baseline scheduled visit with data on weekly mean WI-NRS. Patients will be analysed according to the randomised treatment. Analyses with MFAS will only be carried out if the number of patients in the MFAS differs from the number of patients in the FAS.

#### 4.2.4 Safety Analysis Set (SAS)

All patients who are randomised and dispensed the trial medication at Randomisation/Day 0, excluding patients to whom trial medication is not dispensed or who return all the trial medication unused. Patients will be analysed according to the actual treatment.

#### 4.2.5 Per-Protocol Set (PPS)

A subset of the MFAS patients who completed the trial with WI-NRS data for Week 12 and are deemed to have no important protocol deviations that could interfere with the objectives of this trial. Important deviations of eligibility criteria and other deviations from the protocol will be assessed. Important deviations from the protocol may lead to exclusion of a patient or data points from the PPS, which could have interfered with the administration of the treatment or the evaluation of treatment effect. All such decisions will be identified and documented before the final trial database is unblinded. Important protocol deviations may include, but are not limited to, randomized treatment not taken, medication non-compliance (<80%), missing 3 or more consecutive application days, and intake of prohibited concomitant therapies, which may have an impact on the primary endpoint.

#### 4.2.6 Usage of Analysis Populations

The SAS will be used for all safety analyses. FAS, MFAS, and PPS will be used for efficacy analyses. The SS will be used for analyses of disposition, screened failures, and general comments.

### 4.3 Subgroups and Confounding Factors for Analysis

The mixed model for repeated measures (MMRM) for continuous endpoints (primary and secondary) will be adjusted by menopausal status at baseline, ICIQ-UI-SF score at baseline, and the respective baseline

value of the endpoint being modelled. Similarly for the two binary secondary endpoints, which will be analyzed using a logistic regression at Week 12, the models will be adjusted by menopausal status at baseline, ICIQ-UI-SF score at baseline, and the baseline value for each scale the binary endpoint is derived from (WI-NRS or WP-NRS).

## 4.4 Time Points and Time Periods

### 4.4.1 Periods, Visits and Study Days

The screening period will last from Screening 1 Visit to Baseline visit (Week 0, Day 0). The treatment period will last from randomisation (Week 0) to end of treatment (Week 12 or EoT). The follow-up period will last from end of treatment (Week 12 or EoT) to end of follow-up (Week 14).

A total of eleven visits are planned for each patient (six of these will be in-clinic, 4 phone calls, and the follow-up visit either in-clinic or a phone call). The in-clinic visits will be held at Screening 1, Baseline visit, Weeks 1, 4, 8, and 12, with a follow-up visit at Week 14 (either in-clinic or phone visit). The phone visits will be held at Screening 2, Weeks 3, 7 and 11. The reference date is the date of first treatment; from this, for each visit, actual study days will be derived as the time passed in number of days since the reference date plus 1. Further unscheduled visits may be done as deemed necessary.

### 4.4.2 Dates

Start and end dates, and the dates of last study drug application and last contact will be related to Day 1, given as *study day*. Negative study days indicate dates before the Baseline visit (Week 0)).

It is assumed that treatment in the treatment period occurs from the first dispense of IMP till the last IMP returned, unless otherwise reported.

### 4.4.3 Identification of Baseline Values

In general, baseline values for each variable are the values reported at baseline (Baseline visit, Day 0). If values at baseline are missing, values at the Screening 1 Visit will be used as baseline values, if available.

### 4.4.4 Definitions of Change from Baseline

Changes from baseline are defined as post-baseline value minus baseline value. Reductions are negative changes. Percentage changes from baseline are defined as 100 times changes from baseline divided by the baseline value.

### 4.4.5 Treatment Emergency of Adverse Events

In general, treatment emergent AEs are defined as events starting on or after the day of start of IMP that were absent pre-treatment, or events present prior to the first dose but increased in severity after the first dose. Otherwise, an AE is not treatment-emergent.

### 4.4.6 Treatment Relation of Concomitant Medication

A medication or therapy is related to treatment by timing. It is prior, prior ongoing, or concomitant as defined in Section 2.4.4 above.

## 4.5 Units and Unit Conversion

### 4.5.1 Date and Time Formats and Conversions

Dates are recorded by day, month and year. For imputation of partial dates, see Section 4.7.1 below. Days are calculated following rules in Sections 4.4.1, 4.4.2 and 4.6.1.

It is assumed that no unit conversion is required.

## 4.6 Data Derivations

For the derivation of total and sum scores in efficacy endpoints see Section 2.4.1 above.

### 4.6.1 Durations

Time durations, i.e. lengths of time periods, will be derived as end date minus start date plus 1 day in days.

### 4.6.2 Visit Windowing

Post-baseline in-clinic visits are to be held at Weeks 1, 4, 8, and 12 within the following days from target day: study day  $7\pm 1$ ,  $28\pm 4$ ,  $28\pm 4$ ,  $56\pm 4$ ,  $84\pm 4$ . In addition, unscheduled EoT visits will also be taken into account, if need be.

Non-overlapping visit windows are defined as follows:

Table 4 Analysis visit time windows

Assessments at following Weeks	Time window	Start of time window (study days)	End of time window (study days)
1, 4, 8, 12	Week 1 visit	1	17
	Week 4 visit	18	42
	Week 8 visit	43	70
	Week 12 visit	71	91
4, 8, 12	Week 4 visit	1	42
	Week 8 visit	43	70
	Week 12 visit	71	91

Primary and secondary efficacy endpoints will be summarized and analysed by *analysis visits*. For the visits shown in the table above, analysis visits are defined as the visits held closest to the target day within the analysis visit window as defined above. Any other visits within the same visit window will not be considered for analysis of primary or secondary efficacy endpoints. If the time distances of two visits from the target day are identical, the later visit is selected for analysis.

Other efficacy endpoints and safety endpoints will be summarized and analysed by nominal visits as appropriate.

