1.3 Schedule of assessments (SoA)

Table 1: Schedule of assessments

Trial Period	Screening		Treatment									FU
Visit Number ¹ (Visit name)	1 (Screening1)	2 (Screening 2)	3 (Baseline)	4	5	6	7	8	9	10 (EoT ²)	11 (FU ³)	
Trial Week			0	1	3	4	7	8	11	12	14	
Days from Baseline Visit Window	-28 to -8 NA	(-11 to) -8	0 NA	7 ±1	18 ±2	28 ±4	46 ±2	56 ±4	74 ±2	84 ±4	98 ±4	
Visit type ⁴	In-Clinic	Phone	In-Clinic	In-Clinic	Phone	In-Clinic	Phone	In-Clinic	Phone	In-Clinic	In-Clinic/ Phone	
Informed Consent ⁵	X											
Demographics	X											
Eligibility Assessment	X		X									
Medical History	X											
Menopausal status and Menstrual cycle status			X							X		
Prior & concomitant therapies ⁶	X		X	X	X	X	X	X	X	X	X	
VLS History	X											
VLS Patient Journey ⁷	X											
ICIQ-UI-SF			X							X		
WI-NRS and WP- NRS – in-clinic assessment ^{7,8}	X		X	X		X		X		X		

Trial Period	Screening		Treatment									FU
Visit Number ¹ (Visit name)	1 (Screening1)	2 (Screening 2)	3 (Baseline)	4	5	6	7	8	9	10 (EoT ²)	11 (FU ³)	
Trial Week			0	1	3	4	7	8	11	12	14	
Days from Baseline Visit Window	-28 to -8 NA	(-11 to) -8	0 NA	7 ± 1	18 ± 2	28 ± 4	46 ± 2	56 ± 4	74 ± 2	84 ± 4	98 ± 4	
Visit type ⁴	In-Clinic	Phone	In-Clinic	In-Clinic	Phone	In-Clinic	Phone	In-Clinic	Phone	In-Clinic	In-Clinic/ Phone	
WI-NRS and WP- NRS Diary (Handout) ⁹	X		X	X		X		X				
WI-NRS and WP- NRS diary completion reminder ⁴		X	X		X		X		X			
WI-NRS and WP- NRS Diary (return & review) ¹⁰			X	X		X		X		X		
WPP-NRS – in-clinic assessment ⁸	X		X			X		X		X		
Patient's Global Impression of Change (PGIC) ⁷						X		X		X		
Patient's rating of importance of improvement ⁷						X		X		X		
VQLI ⁷			X			X		X		X		
Skindex-29 ⁷			X			X		X		X		
Imaging of VLS ¹¹	X		X	X		X		X		X		
VASSI	X		X	X		X		X		X		
CGA	X		X	X		X		X		X		

Trial Period	Screening		Treatment									FU
Visit Number ¹ (Visit name)	1 (Screening1)	2 (Screening 2)	3 (Baseline)	4	5	6	7	8	9	10 (EoT ²)	11 (FU ³)	
Trial Week			0	1	3	4	7	8	11	12	14	
Days from Baseline Visit Window	-28 to -8 NA	(-11 to) -8	0 NA	7 ±1	18 ±2	28 ±4	46 ±2	56 ±4	74 ±2	84 ±4	98 ±4	
Visit type ⁴	In-Clinic	Phone	In-Clinic	In-Clinic	Phone	In-Clinic	Phone	In-Clinic	Phone	In-Clinic	In-Clinic/ Phone	
CGIC				X		X		X		X		
Physical examination ¹²	X		X							X	(X)	
Vital signs ¹³			X							X	(X)	
Urine pregnancy test ¹⁴	X		X	X		X		X		X	(X)	
Randomisation			X									
Application Diary (Handout)			X	X		X		X				
Application Diary (Return and review) ¹⁰				X		X		X		X		

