6.1.2 Dosing and administration

MC2-25 cream, or MC2-25 vehicle must be applied after each toilet visit following urination (during day and night) starting on the day of the Baseline visit. The MC2-25 cream, or MC2-25 vehicle should be applied by the patient in a thin saturating layer to the vulvar region (i.e., vulvar region includes clitoris and periclitoral skin, interlabial sulci, labia minora, posterior fourchette and perineum, anal and perianal skin). Approximately one fingertip-unit (FTU), roughly corresponding to 0.5 g cream is to be used after each toilet visit (during night and day). The vulvar region may be gently cleaned with water and dabbed dry with toilet paper or a clean cloth before each application of the trial treatment. Assuming, a maximum of 12 toilet visits are needed over a period of 24 hours, the maximum daily dose is expected to be around 6.0 g. A treatment application manual will be available for patients.

Reference is made to Section 4.2 for the rationale behind the dosing-regimen.

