## 2 Study Design and Objectives

### 2.1 Study Design

This is a multicentre, phase 2, randomised, double-blind, 2-arm, parallel-group and vehicle-controlled trial in VLS conducted in Denmark. Random allocation to one of two parallel treatment groups is in a 1:1 ratio to MC2-25 cream or MC2-25 vehicle.

A total of 40 patients are planned to be enrolled, randomised and observed until final evaluation and completion. Patients prematurely terminating the trial will not be replaced. Following protocol amendment #3, and the associated protocol v4.0, recruitment was terminated at 33 patients.

The maximum trial duration for each patient will be at most 18 weeks and includes a screening period of up to 4 weeks (allowing for wash out of other treatments and emollients before baseline as/if applicable), a 12-week treatment period, and a 2-week post-treatment follow-up (FU) period.

A total of eleven visits are planned (six of these will be in-clinic, 4 by phone, and the follow-up visit either in-clinic or by phone). The in-clinic visits will be held at Screening 1 (Visit 1, Day -28 to -8), Baseline (Visit 3, Week 0, Day 0), Visits 4, 6, and 8 at Weeks 1, 4 and 8, respectively, planned for Days  $7\pm1$ ,  $28\pm4$ , and  $56\pm4$ , respectively, Visit 10 as end of treatment Visit (Week 12, Day  $84\pm4$ , or at early termination). The follow-up visit at Visit 11 (Week 14, Day  $98\pm4$ ) will be either an in-clinic or a phone visit, depending on the follow up assessments considered necessary by the investigator. The phone visits will be held at Screening 2 (Visit 2, Day -11 to -8), Visits 5, 7, and 9 at Weeks 3, 7 and 11, respectively, planned for Days  $18\pm2$ ,  $46\pm2$ , and  $74\pm2$ , respectively. An unscheduled visit can be conducted to perform any of the post-baseline assessments or procedures included in the schedule of assessments (SoA) if deemed necessary by the Investigator. If Screening 1 visit is performed on Day -8, then Screening 2 visit will be omitted. For a visit schedule, see CTP Section 1.3 [1].

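### SAP 4.6.2 writes its visit windows in Day-0 numbers but calls them study days, which SAP 4.4.1 counts from 1, so targets and boundaries sit one day early and Baseline is not barred by number

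*SAP*

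**What the plan says.** Two day scales are in use.

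- **Counting from 1.** SAP 4.4.1: "The reference date is the date of first treatment", and "actual study days will be derived as the time passed in number of days since the reference date plus 1". Protocol 6.1.2 has the cream applied "starting on the day of the Baseline visit". A woman who follows the protocol is therefore at study day 1 on her Baseline visit. SAP 4.4.2 also relates dates to Day 1.
- **Counting from 0.** The protocol's schedule of assessments has a row headed "Days from Baseline Visit Window", with Baseline at 0 and Weeks 1, 4, 8 and 12 at 7, 28, 56 and 84. SAP 2.1 repeats this: Baseline is Day 0, with "Visits 4, 6, and 8 at Weeks 1, 4 and 8, respectively, planned for Days" 7±1, 28±4 and 56±4, and Week 12 on Day 84±4.

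SAP 4.6.2 takes 7, 28, 56 and 84 as targets and calls them study days. Both boundary columns of Table 4 carry the same unit. The windows are Week 1 = 1-17, Week 4 = 18-42, Week 8 = 43-70 and Week 12 = 71-91. For endpoints assessed only at Weeks 4, 8 and 12, such as Skindex-29, Week 4 is 1-42. Within a window, "analysis visits are defined as the visits held closest to the target day within the analysis visit window as defined above". Ties go to the later visit, and other visits in the window are not used for the primary and secondary endpoints.

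**The concern.** If Baseline is study day 1, the protocol's Days 7, 28, 56 and 84 are study days 8, 29, 57 and 85. A programmer who derives study day by SAP 4.4.1 and applies Table 4 as printed will have every target and boundary one day early. A programmer who recognises the numbers as days from Baseline will build a different dataset. A final SAP should not leave both options open for the windows behind the primary and secondary endpoints.

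Two things are at stake. First, visits on a few boundary days change window, and at Week 12 this can turn an observed value into a missing one. Secondly, study day 1 lies inside the first window of both schedules, and no number in the rule keeps it out. A Baseline record labelled Week 1 would carry a change of exactly 0. It would count as observed, so it would not be imputed, and it would enter both the repeated-measures model and the visit-by-visit imputation of later weeks.

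**Working it through.** **1. Reproduce Table 4.** Take the upper bound as the midpoint of adjacent targets, rounded down, open the first window on the day after Baseline, and close the last at target + 7. With targets 7, 28, 56 and 84:

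- (7+28)/2 = 17.5, giving 17
- (28+56)/2 = 42
- (56+84)/2 = 70
- 84+7 = 91

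This gives 1-17, 18-42, 43-70 and 71-91, and 1-42 for the Week 4/8/12 schedule. It matches Table 4 exactly, so the table fits the Day-0 scale.

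**2. The same rule on the SAP 4.4.1 scale.** With targets 8, 29, 57 and 85, opening at study day 2:

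- (8+29)/2 = 18.5, giving 18
- (29+57)/2 = 43
- (57+85)/2 = 71
- 85+7 = 92

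The windows are 2-18, 19-43, 44-71 and 72-92, with 2-43 for Skindex-29 Week 4. Every boundary moves by +1.

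**3. Which days change window.** Study day = days from Baseline + 1.

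| Days from Baseline | Study day | Window if Table 4 means days from Baseline | Window as written |
|---|---|---|---|
| 0 | 1 | none | Week 1 (Week 4 for Skindex-29) |
| 17 | 18 | Week 1 | Week 4 (Skindex-29: Week 4 either way) |
| 42 | 43 | Week 4 | Week 8 |
| 70 | 71 | Week 8 | Week 12 |
| 91 | 92 | Week 12 | none |

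Day 17 is 10 days from Day 7 and 11 from Day 28, so the move takes it away from its nearer target. Days 42 and 70 are each 14 days from both neighbouring targets, so neither allocation is clearly wrong. Day 91 becomes missing. SAP 4.7.2 then imputes the continuous endpoints and sets the four responder endpoints to no improvement. One responder lost this way is 1/16 = 6.25 or 1/17 = 5.9 percentage points of her arm.

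**4. Visits on schedule.** Days 6-8, 24-32, 52-60 and 80-88 become study days 7-9, 25-33, 53-61 and 81-89. All of them fall in the correct Table 4 window.

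**5. Baseline under a purely numeric reading.** Baseline (study day 1) is 6 days from target 7.

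- A real Week 1 visit on study day 13 ties at 6 and wins as the later visit.
- On study days 14-17 (Days 13-16 from Baseline) a real visit is 7 to 10 days away and loses to Baseline.
- Baseline is also selected if there is no other visit in the window.
- For Skindex-29, Baseline is 27 days from target 28. Every study day from 2 to 42 is nearer, so Baseline is selected only if no other Skindex-29 visit falls there.

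**6. Size if that reading were programmed.** With 16 women per arm, k women missing from the first window shrink that visit's arm mean change by k/16: 6.25% for one and 12.5% for two. The carry-through to Week 12 for women lost after Baseline is roughly |mean Week 1 change| × slope of Week 12 on Week 1 × k/16. The documents give neither the change nor the slope. Assuming a change of 0.5 to 1.5 points and a slope of 0.5 to 0.8:

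- k = 1: 0.5×0.5/16 = 0.02 to 1.5×0.8/16 = 0.08 points
- k = 2: 0.03 to 0.15 points

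**The case against.** The strongest reply is that the SAP never intends Baseline to be a candidate. Section 4.6.2 opens with post-baseline in-clinic visits, and its selection sentence is limited to the visits listed in the table, which are Weeks 1, 4, 8 and 12. SAP 4.4.3 makes the Baseline visit the source of the baseline value, and 4.4.4 defines change as a post-baseline value less that baseline. SAP 4.7.2 imputes post-baseline data, and Protocol 9.4.2.1 models post-baseline assessments. This largely stands. A reader might infer that the SAP plans to analyse Baseline as a Week 1 outcome, making the imputation a partial baseline-carried-forward. The documents do not support that, because it requires ignoring all of these passages. Nor could Baseline reach the responder endpoints, which are analysed at Week 12 (study days 71-91). What remains is that the exclusion is implied and the numeric rule does not state it.

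A second reply is that the SAP's numbering is mixed. It labels Baseline Day 0 in several places, and SAP 4.4.2 says "Negative study days indicate dates before the Baseline visit", whereas the plus-1 formula gives 0 for the day before Baseline. That is true, but it is a further reason to state the scale. It does not reconcile 4.6.2 with the one formula the SAP gives for deriving study days.

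A third reply is that boundary days are rare. This also stands. Day 17 is 9 days past the Week 1 visit window and 7 before the Week 4 window. Days 42 and 70 are 10 days from any window, and Day 91 is 3 days late. But 4.6.2 expressly admits unscheduled end-of-treatment visits, which can fall on any day.

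**Conclusion.** The mismatch is real: the targets and boundaries in 4.6.2 are one day early on the SAP's own study-day scale. The clear errors are Day 17, assigned to the farther visit, and Day 91, dropped from Week 12. Days 42 and 70 change window without a clear right answer. Where two visits compete within a window, the early target can also change which is chosen. Baseline is excluded by implication but not by number.

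The Week 12 comparison is touched directly only by visits exactly 70 or 91 days after Baseline, or by competing visits near the target. The expected effect is small, and nil if no such visit occurs and Baseline is treated as ineligible. The 0.02 to 0.15 point range applies only under the purely numeric reading and the assumed inputs above.

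The point rests on first application on the Baseline date, as the protocol requires. For a woman who starts a day later, study day equals days from Baseline and the mismatch disappears. This is a minor correction to the specification and does not threaten the primary analysis.

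**What to change.** Amend SAP 4.6.2 in one of two equivalent ways:

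- Restate it on the SAP 4.4.1 scale: targets 8, 29, 57 and 85; windows Week 1 = 2-18, Week 4 = 19-43 (2-43 for Skindex-29), Week 8 = 44-71, Week 12 = 72-92.
- Keep the printed numbers, relabel them as days from Baseline with Baseline = Day 0, and derive the windowing day as visit date minus Baseline date, without the plus 1.

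In either case add a sentence that the Baseline visit is never eligible as a post-baseline analysis visit. The cost is one table and one or two sentences, with no new data and no effect on conduct.

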9.2 Sample size determination

Sixty two (62) patients will be screened. 33 patients will be randomised in a 1:1 ratio of MC2-25 cream to MC2-25 vehicle. For a two-sided test with a 5% level of significance and an effect size of 1 standard deviation, this sample size will provide adequate power ($\geq 78\%$) to compare mean change in mean weekly WI-NRS from Baseline to Week 12 between MC2-25 cream and MC2-25 vehicle with 16 to 17 patients per treatment group.

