## 5.3 Multiplicity Adjustment and Estimands

No multiple testing adjustment will be employed in this study.

The primary endpoint will be analyzed by different estimands, following a treatment policy strategy with imputation (primary estimand) (Section 4.7.2), a treatment policy strategy without imputation (secondary estimand), and a while on treatment strategy without imputation (tertiary estimand).

For the primary estimand, all available data will be used, regardless of treatment and treatment adherence, with missing data imputed as described in Section 4.7.2. For the secondary estimand, all available data will be used, regardless of treatment and treatment adherence, and missing data will not be imputed.

For the tertiary estimand, all available data will be included up to 7 days after the last treatment intake, regardless of treatment and treatment adherence, and missing data will not be imputed. Data more than 7 days after the last treatment intake is invalid and will not be used.

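### The SAP's visit-window rule selects a visit rather than a value, so when two visits share the Week 12 window an observed weekly itch mean can be dropped; that window also closes only 2 days after the latest on-time visit.

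*SAP*

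**What the plan says.** SAP 4.6.2 assigns primary and secondary efficacy data to analysis visits. In its words, "analysis visits are defined as the visits held closest to the target day within the analysis visit window as defined above". Ties go to the later visit. On everything else in the window it says: "Any other visits within the same visit window will not be considered for analysis of primary or secondary efficacy endpoints". The Week 12 window in SAP Table 4 is study days 71 to 91, and no window covers later days. The section adds that unscheduled End-of-Treatment visits can be taken into account if needed, without saying when.

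SAP 4.7.2 classes data not considered for analysis as invalid and multiply imputes missing and invalid data in the primary analysis on the full analysis set. For the 3- and 4-point responder endpoints, a missing endpoint counts as no improvement.

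SAP 4.4.1 defines study day as days since first treatment plus 1. SAP 4.6.2 nevertheless gives the targets as study days 7, 28, 56 and 84, which are the protocol's days from baseline, and it lists the Week 4 target twice.

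**The concern.** The rule picks a visit by date alone. If the chosen visit has no weekly mean, a usable mean elsewhere in the window is excluded and a model-based value or a non-response takes its place.

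Two visits in the Week 12 window are possible under the protocol. Section 7.1 asks for the Week 12 assessments at treatment discontinuation and then encourages attendance at the remaining visits. The schedule of assessments also allows unscheduled visits. It shows diary return but no diary handout at Visit 10 (EoT), so a second visit soon afterwards would normally have no new diary.

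Separately, the early closing of the Week 12 window can exclude a moderately late Visit 10 with a complete diary. With 33 patients, each lost Week 12 value is about 6% of an arm (1/17 = 5.9%, 1/16 = 6.3%).

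**Working it through.** **1. The plan's own power.** Inputs from protocol 9.2: "For a two-sided test with a 5% level of significance and an effect size of 1 standard deviation", "with 16 to 17 patients per treatment group", stated power at least 78%. Two-sample t-test power is P(|T| > t(0.975; n1+n2−2)), where T is noncentral t with noncentrality d/√(1/n1 + 1/n2) and d = 1.

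| Week 12 values per arm | Noncentrality | Critical t | Power |
|---|---|---|---|
| 17 / 16 (none lost) | 2.871 | 2.040 | 79.4% |
| 16 / 16 (one lost) | 2.828 | 2.042 | 78.1% |
| 16 / 15 (two lost) | 2.782 | 2.045 | 76.7% |
| 15 / 15 (three lost) | 2.739 | 2.048 | 75.3% |

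The stated figure is reproduced. The first lost value costs 79.4 − 78.1 = 1.3 points.

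**2. Room after an on-time visit.** Protocol days are converted to study days by adding 1 (SAP 4.4.1, with first treatment on the day of the Baseline visit) and set against SAP Table 4.

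| Visit | Protocol days | Study days | SAP window | Days left after latest on-time visit |
|---|---|---|---|---|
| Week 1 | 6–8 | 7–9 | 1–17 | 17 − 9 = 8 |
| Week 4 | 24–32 | 25–33 | 18–42 | 42 − 33 = 9 |
| Week 8 | 52–60 | 53–61 | 43–70 | 70 − 61 = 9 |
| Week 12 | 80–88 | 81–89 | 71–91 | 91 − 89 = 2 |

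Every on-time Week 12 visit is kept. A Visit 10 on study day 92 or later has no window. The follow-up visit (Day 98±4) falls on study days 95 to 103 and has no scheduled diary, so the early close avoids no overlap with other diary data.

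**3. Two visits in one window (illustrations).** Both assume that a weekly mean belongs to the visit at which its diary is returned.

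- An EoT visit on study day 77 with a diary kept on days 70–76, then Visit 10 on study day 85 without a diary. Distances from target 84 are 7 and 1. Day 85 is selected, and the day-77 mean is excluded.
- An on-time Visit 10 on study day 81 with a diary, then an unscheduled visit on study day 84 without one. Distances are 3 and 0. Day 84 is selected, and the Visit 10 mean is excluded. This needs an ordinary unscheduled visit to count as a candidate, which the SAP does not settle.

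**4. The target-day scale.** For visits on study days 81 and 88, the distances from 84 are 3 and 4, so day 81 is chosen. From 85 they are 4 and 3, so day 88 is chosen. The scale matters only when two visits share a window.

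**The case against.** The strongest reply is that this rarely bites. On-schedule visits are safe, and a Visit 10 on study day 92 is at least 3 days outside the protocol's own visit window. The two-visit case also fits the diary schedule loosely. Diaries are planned only for the 7 days before an in-clinic visit, so an unplanned early EoT visit would often have no current weekly mean. All of this stands, and it limits the size of the point.

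It can also be said that Table 4 is organised by assessment, that EoT visits may be taken into account, and that SAP 5.7 leaves detail to programming specifications. These make a sensible implementation possible but do not supply the rule. No sentence ties selection to a non-missing value, and the exclusion of other visits is explicit. The modified full analysis set, by contrast, does require a visit with weekly mean data.

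A reader might infer that the windows contradict the treatment-policy estimand, since SAP 5.3 says "all available data will be used, regardless of treatment and treatment adherence". The documents do not support that. The sentence mainly concerns intercurrent events. The endpoint is change to Week 12, so some time window is part of defining it, and late attendance is not an intercurrent event.

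A reader might also want the Week 12 limit removed. Protocol 7.3 allows an EoT visit up to 30 days after discontinuation, so with a last dose on study day 85 a value from day 85 + 30 = 115 could be labelled Week 12. A bound is needed.

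**Conclusion.** The point holds as a cheap correction to a stated rule. SAP 4.6.2 can exclude an observed Week 12 mean when two visits share the window and the closer one lacks the value, and it closes that window unusually early. It does not follow that the plan routinely loses Week 12 data.

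The documents give no rate of late or duplicate visits. An assumed range of 0 to 3 patients of 33 takes t-test power from 79.4% to 75.3%, and zero is plausible. In the responder analyses, each discarded responder lowers that arm's rate by about 6 percentage points.

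The t-test figures are a rough gauge of the planned mixed model with multiple imputation. Simplified simulations of arm-specific imputation, with one value lost in each arm and assumed between-visit correlations of 0.3 to 0.7, gave losses of roughly 3 to 10 points. That spread reflects correlations the documents do not give and requires two losses, so the conclusion does not rest on it.

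**What to change.** Before unblinding, make three changes to SAP 4.6.2:

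1. Reword the selection rule: *For each endpoint, the analysis visit is the visit in the window with a non-missing value of that endpoint held closest to the target day.*
2. State the target days on the study-day scale of SAP 4.4.1 (8, 29, 57, 85), and delete the repeated Week 4 entry.
3. Extend the Week 12 upper limit to a stated bound that admits a moderately late Visit 10. Study day 94, the day before the follow-up visit window opens, is one choice. It leaves 94 − 89 = 5 days after the latest on-time visit.

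The cost is a few lines of text and one limit, in both Week 12 rows of Table 4. The downside is that a few late Week 12 values, some collected after treatment ended, enter the analysis. Fixing the rule before unblinding ensures that the choice between visits cannot depend on results.
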